7.1.2. Study Drug Restart or Rechallenge After Liver Stopping Criteria Are Met

Study drug restart/rechallenge after liver chemistry stopping criteria are met is allowed in this study. If the subject meets liver chemistry stopping criteria, do not restart/rechallenge the subject with study drug unless:

- Sponsor/medical monitor approval is granted
- Ethics and/or IRB approval is obtained, if required

NOTE: If study drug was interrupted for suspected study drug-induced liver injury, the subject should be informed of the risk of death, liver transplantation, hospitalization, and jaundice before resumption of dosing.

Refer to Section 10.5 Liver Safety: Required Actions and Follow-up Assessments and Study Drug Restart/Rechallenge Guidelines for details on the restart/rechallenge process.

If sponsor/medical monitor approval to restart/rechallenge the subject with study drug is **not granted**, then the subject must permanently discontinue study drug and may continue in the study for protocol-specified study assessments.

¹Liver Safety: Required Actions and Follow-up Assessments can be found in Section 10.5.

²If ALT or AST ≥ 3 x ULN, increase monitoring of liver chemistries to twice weekly.

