- b) Failure rate of < 1% per year when used consistently and correctly. Typical use failure rates differ from those when used consistently and correctly.
- c) Considered effective but not highly effective failure rate of $\geq 1\%$ per year.

Note: Periodic abstinence (calendar, symptothermal, postovulation methods), withdrawal (coitus interruptus), spermicides only, and lactational amenorrhea method are not acceptable methods of contraception. Male condoms and female condoms should not be used together (due to risk of failure from friction).

10.5. Liver Safety: Required Actions and Follow-up Assessments and Study Drug Restart/Rechallenge Guidelines

Phase 2 liver chemistry stopping criteria are designed to assure subject safety and to evaluate liver event etiology. The guidelines provided below are based on the European Association for the Study of the Liver Clinical Practice Guidelines: Drug-induced Liver Injury. (2019) and FDA 2009 Guidance for Industry Drug-Induced Liver Injury: Premarketing Clinical Evaluation.

Phase 2 Liver Chemistry Stopping Criteria and Follow-Up Assessments

Liver Chemistry Stopping Criteria							
ALT or AST-absolute	LT or AST-absolute Alanine aminotransferase (ALT) or aspartate aminotransferase (AST) ≥ 5 x upper limit of normal (ULN)						
ALT or AST Increase	ALT or AST ≥ 3 x ULN persists for ≥ 4 weeks						
Bilirubin ^{1,2}	abin ^{1,2} ALT or AST \geq 3 x ULN and total bilirubin \geq 2 x ULN (> 35% direct bilirubin)						
INR ²	ALT or AST \geq 3 x ULN and international normalized ratio (INR) > 1.5						
Cannot Monitor	ALT or AST ≥ 3 x ULN and cannot be monitored twice weekly for 4 weeks						
Symptomatic ³ ALT or AST \geq 3 x ULN associated with symptoms (new or worsening) believed to be related to liver injury or hypersens							
Require	ed Actions, Monitoring, a	nd Follow-up Assessments					
Acı	tions	Follow-Up Assessments					
Immediately discontinuately discontinuate	, c	• Viral hepatitis serology ⁴					
• Report the event to the within 24 hours.		• Obtain blood sample for pharmacokinetic (PK) analysis after the most recent dose ⁵ .					
• Complete a serious a if the event met the c	dverse event (SAE) CRF riteria for an SAE. ²	Obtain serum creatine phosphokinase					
in the Follow-Up As		(CPK), lactate dehydrogenase (LDH), gamma-glutamyltransferase [GGT], glutamate dehydrogenase [GLDH],					

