- Liver biopsy may be considered and discussed with local specialist if available, for instance:
 - In subjects when serology raises the possibility of autoimmune hepatitis (AIH)
 - In subjects when suspected drug-induced liver injury

progresses or fails to resolve on withdrawal of study drug
 In subjects with acute or chronic atypical presentation
If liver biopsy conducted provide biopsy information.

- 1. Serum bilirubin fractionation should be performed if testing is available. If serum bilirubin fractionation testing is unavailable, **record the absence/presence of detectable urinary bilirubin on dipstick** which is indicative of direct bilirubin elevations suggesting liver injury.
- 2. All events of ALT or AST ≥ 3 x ULN and total bilirubin ≥ 2 x ULN (> 35% direct bilirubin) or ALT or AST ≥ 3 x ULN and INR > 1.5 may indicate severe liver injury (possible 'Hy's Law') and must be reported to sponsor in an expedited manner and as an SAE if SAE criteria met (excluding studies of hepatic impairment or cirrhosis). The INR stated threshold value will not apply to subjects receiving anticoagulants.
- 3. New or worsening symptoms believed to be related to liver injury (such as fatigue, nausea, vomiting, right upper quadrant pain or tenderness, or jaundice) or hypersensitivity (such as fever, rash, or eosinophilia).
- 4. Record the date/time of the PK blood sample draw and the date/time of the last dose of study drug prior to the blood sample draw on the CRF. If the date or time of the last dose is unclear, provide the subject's best approximation. If the date/time of the last dose cannot be approximated OR a PK sample cannot be collected in the time period indicated above, do not obtain a PK sample. Instructions for sample handling and shipping are in the Study Laboratory Manual.

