6.7.3.1. Liver toxicity review

Potential liver toxicity will be assessed by listing subjects who met potential drug induced liver injury (DILI) criteria as described in the protocol and by summarizing subjects who met Hy's Law.

Subjects who met any (one or more) of the following criteria will be included in a listing for consideration of DILI:

- ALT or AST $\geq 5 \times ULN$ at any time
- ALT or AST \geq 3 x ULN at all (2 or more) assessments in a span of \geq 4 weeks
- ALT or AST \ge 3 x ULN and total bilirubin \ge 2 x ULN (>35% direct bilirubin) simultaneously at any time
- ALT or AST \geq 3 x ULN and international normalized ratio (INR) \geq 1.5 simultaneously at any time

- ALT or AST \ge 3 x ULN at any time during the study and weekly assessments after this finding are not available for at least 4 weeks
- ALT or AST ≥3 x ULN associated with symptoms (new or worsening) believed to be related to liver injury or hypersensitivity at any time

To determine subjects who meet the last criterion, a listing of all subjects who have at least one ALT or AST \geq 3 x ULN at any time, and who do not meet any of the first five criteria, will be reviewed by qualified medical professionals along with a listing of all AEs reported by such subjects. In coordination with the investigator, the medical professionals will assess whether any AE is believed to be related to liver injury or hypersensitivity and, if so, whether the elevated ALT or AST is in temporal association with the AE. Any subjects who meet these criteria will be included on a memo that will be filed in the TMF prior to database lock and unblinding, and included in the listings. For subjects who meet any of the six criteria, all LFT results at any time during the study will be listed, sorted by subject and date. Listing will include subject, treatment assignment, ALT, AST, bilirubin and INR, along with specific criterion met.

Subjects who meet the criteria for Hy's Law will be displayed in shift tables. Hy's Law is met when ALT or AST is $\ge 3 \times ULN$, total bilirubin $\ge 2 \times ULN$ and ALP is $< 2 \times ULN$, with all occurring simultaneously (at the same draw). At each assessment, subjects will be classified as meeting Hy's Law or not meeting Hy's Law. The shift tables will be presented as follows:

- Treatment period 1
 - Baseline (meet Hy's Law / not meet Hy's Law)
 - Any time during period 1 (meet Hy's Law at least one time / not meet Hy's Law at any time)

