 - One table presented for each treatment arm (160 mg QW / 160 mg Q2W / combined placebo)
- Treatment period 2
 - Baseline prior to treatment period 1 (meet Hy's Law / not meet Hy's Law)
 - Any time during period 2 (meet Hy's Law at least one time / not meet Hy's Law at any time)
 - One table presented for each treatment arm (160 mg QW / 160 mg Q2W / placebo 160 mg QW / placebo 160 mg Q2W)

Separate Kaplan Meier (KM) analyses plots will be created for time to:

- First instance of meeting Hy's Law
- First instance of ALT or AST $\geq 5 \times ULN$
- First instance of ALT or AST \ge 3 x ULN and total bilirubin \ge 2 x ULN (>35% direct bilirubin) simultaneously

- First instance of ALT or AST \geq 3 x ULN and international normalized ratio (INR) \geq 1.5 simultaneously
- First instance of ALT or AST $\ge 3 \times ULN$ associated with symptoms (new or worsening) believed to be related to liver injury or hypersensitivity at any time

for the study duration (Day 1 through Week 32). In each plot, the subjects taking any treatment with Q2W frequency will be indicated by a solid line. The subjects taking any treatment with QW frequency will be indicated by a dashed line. Separate colors will be used to distinguish subjects randomized to izokibep and those randomized to placebo.

Subjects who do not experience an event will be censored at their last attended assessment. The date/time of onset of the first instance of the event of interest will be used as the date/time of the event in the analysis.

The product-limit estimator at Week 16 and Week 32 will be summarized by treatment group.

If there are < 3 events in a treatment arm for an event, then the KM analysis will not be done.

A listing of all LFT results from all subjects who meet Hy's Law at least one time during the study will be produced, sorted by subject and date. This listing will show subject, treatment assignment, period, ALT, AST, ALP, bilirubin and INR.

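### SAP 6.7.3.1 says its liver-injury listing uses the protocol's criteria, but its INR and monitoring criteria differ from Protocol 10.5

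*SAP*

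**What the plan says.** SAP 6.7.3.1 introduces its listing as covering subjects who met "potential drug induced liver injury (DILI) criteria as described in the protocol", and then gives six criteria.

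- **INR.** The fourth criterion pairs ALT or AST ≥ 3 × ULN with INR ≥ 1.5 and states no exemption. The same section repeats the threshold for a time-to-first-event Kaplan-Meier analysis: "international normalized ratio (INR) \geq 1.5 simultaneously". The stopping-criteria table in Protocol 10.5 has "international normalized ratio (INR) > 1.5", and note 2 to that table adds: "The INR stated threshold value will not apply to subjects receiving anticoagulants".
- **Monitoring.** The fifth criterion is ALT or AST ≥ 3 × ULN where "weekly assessments after this finding are not available for at least 4 weeks". The Cannot Monitor row in Protocol 10.5 applies when a subject with ALT or AST ≥ 3 × ULN "cannot be monitored twice weekly for 4 weeks". The footnote to the stopping algorithm in Protocol 7.1.1 sets the same frequency at that level: "increase monitoring of liver chemistries to twice weekly".

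**The concern.** A listing said to apply the protocol's criteria should identify the subjects who met them. Here it can err in both directions. The listing prints the specific criterion met, so a wider INR rule can record a subject as meeting a protocol stopping criterion that was not met. A laxer monitoring rule can omit a subject who did meet one. At stake is the accuracy of a descriptive safety output. No hypothesis test, alpha allocation or site-level stopping rule depends on it.

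**Working it through.** There is no plan figure to reproduce. The check is a line-by-line comparison.

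| Criterion | Protocol 10.5 | SAP 6.7.3.1 | Agree? |
|---|---|---|---|
| 1. Absolute | ALT/AST ≥ 5 × ULN | Same, at any time | Yes |
| 2. Persistent | ≥ 3 × ULN lasting ≥ 4 weeks | ≥ 3 × ULN at every one of 2 or more assessments spanning ≥ 4 weeks | Yes, made operational |
| 3. Bilirubin | ≥ 3 × ULN and total bilirubin ≥ 2 × ULN, > 35% direct | Same, required at the same time | Yes |
| 4. INR | ≥ 3 × ULN and INR > 1.5; not applied on anticoagulants | ≥ 3 × ULN and INR ≥ 1.5; no exemption | **No** |
| 5. Monitoring | ≥ 3 × ULN and twice-weekly testing not possible for 4 weeks | ≥ 3 × ULN and weekly results lacking for at least 4 weeks | **No** |
| 6. Symptoms | ≥ 3 × ULN with related symptoms | Same, settled by medical review | Yes |

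Two of six differ; 6 − 2 = 4 agree in substance.

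**Is the INR difference a text-extraction fault or a version difference?** Neither is likely. Protocol 10.5 uses > 1.5 repeatedly, and one monitoring branch uses the complement, ≤ 1.5. The SAP uses ≥ 1.5 twice. SAP section 1 lists Protocol 4.0 among its sources, its document history mentions no change to liver criteria, and 6.7.3.1 declares no departure.

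**Whom does the INR rule add?** Among subjects with ALT/AST ≥ 3 × ULN, it adds those with INR exactly 1.5 and those on anticoagulants with INR ≥ 1.5. The second group can exist: Protocol 6.8.2 names warfarin as a drug to consider, and 6.8.4 does not prohibit anticoagulants. The error is over-inclusion only. Few subjects will have an INR, because it is absent from the routine laboratory tables (Protocol Table 4; SAP 6.7.3) and is measured in the liver-event work-up.

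**Whom does the weekly rule omit?** Twice weekly for 4 weeks is 2 × 4 = 8 draws; weekly is 1 × 4 = 4. A subject who could be tested only weekly can meet the protocol's criterion and still escape the SAP's fifth. Going through the other criteria:

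- reaching ≥ 5 × ULN: listed under criterion 1;
- staying ≥ 3 × ULN at the weekly tests over 4 weeks: listed under criterion 2;
- qualifying bilirubin or INR: listed under criterion 3 or 4;
- related symptoms: listed under criterion 6.

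What remains is an asymptomatic subject at 3 to < 5 × ULN, with no qualifying bilirubin or INR, who could not be tested twice weekly and whose weekly values fell below 3 × ULN within the 4 weeks.

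**Do other outputs identify that subject?** In part. Every subject with any ALT/AST ≥ 3 × ULN who meets none of the first five criteria goes to the medical review in 6.7.3.1, although that review decides only the symptom criterion. SAP 6.7.3 lists all laboratory data with out-of-range flags. SAP 6.2 lists reasons for treatment discontinuation, but Protocol 7.1 groups hepatotoxicity under safety concern, so the specific liver criterion need not appear. Protocol 7.1.2 allows restart after a liver stop; a restarted subject is not a permanent discontinuation and would reach the interruption listing in SAP 6.7.2 only through a recorded adverse event.

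**The case against.** The strongest reply is that the listing is a screen for consideration of liver injury, so erring wide on INR is cautious. The INR value and the criterion met are printed, and concomitant medications are listed, so a reader can identify an INR of exactly 1.5 or an anticoagulated subject. Exempting anticoagulated subjects makes that criterion less sensitive. The claim to follow the protocol introduces the listing, not the Kaplan-Meier events, and the section's Hy's Law definition adds an ALP condition that Protocol 10.5 lacks. The plot may never be produced: "If there are < 3 events in a treatment arm for an event, then the KM analysis will not be done". Finally, whether a subject cannot be monitored is a site judgment that no laboratory rule reproduces exactly.

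Most of this stands as an argument about consequence. It does not answer the text: the SAP claims identity with criteria that it changes, and it does not call the change deliberate. The Kaplan-Meier INR event mirrors the listing criterion, so correcting only one would leave the section inconsistent with itself.

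A reader might infer that every subject at 3 to < 5 × ULN with only weekly results is lost. The documents do not support that, because criterion 2, the medical review and the laboratory listings cover all but the narrow group above. Nor do fewer than twice-weekly results show that the Cannot Monitor criterion was met. Protocol 10.5 ends twice-weekly testing when the abnormality resolves, normalizes or returns to baseline. Where bilirubin and INR are not raised, it also permits less frequent testing once values are stable, or once drug is stopped and the subject is asymptomatic.

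**Conclusion.** The mismatch is real: two of six criteria differ from those the SAP says it uses. The INR rule can attribute a criterion to subjects with INR exactly 1.5 or on anticoagulants. The weekly rule can omit from the final listing only the narrow asymptomatic group whose values fall below 3 × ULN within 4 weeks. The effect is descriptive and likely very small. That judgment rests on INR being measured mainly in liver work-ups and on the overlap with the other criteria; the documents give no expected number of affected subjects.

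A reader might go further and infer that the Kaplan-Meier estimates would be distorted, or that sites would stop drug on different grounds. Neither follows. The documents do not indicate that any INR events will occur, and sites act on Protocol 7.1.1 and 10.5, not on the SAP. This is a minor point, worth correcting because the correction is cheap.

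**What to change.** In SAP 6.7.3.1:

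- **(a) INR.** In the listing and in the Kaplan-Meier event, use INR > 1.5 and do not apply the criterion to subjects receiving anticoagulants.
- **(b) Monitoring.** In the fifth criterion, replace weekly with twice-weekly. Describe it as a data proxy for the protocol's Cannot Monitor criterion, and do not count time after the abnormality has resolved, normalized or returned to baseline. Also list any subject reported to the sponsor as stopped under the protocol's liver criteria, which captures actual Cannot Monitor stops without relying on the proxy.

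The cost is three lines of SAP text (two in the listing, one in the Kaplan-Meier list), one added listing rule and slightly more programming. The added rule should draw on the liver-event reports, since the recorded discontinuation reason may not name the criterion. The downside is possibly a few more subjects in a descriptive listing, because the proxy does not reproduce every circumstance in which the protocol lets testing become less frequent.

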5.1.3. Treatment Period

Data collected on Day 1 will be assigned to the Treatment Period unless the time (HH:MM) of data collection and time (HH:MM) of the first dose of study drug are both recorded and the data collection time is before the time of the first dose of study drug. In this case, the assessment will be assigned to the screening period. If the time (HH:MM) of data collection is not recorded but the protocol and/or CRF includes an instruction to the effect that all Day 1 assessments are to be performed prior to the first dose of study drug, the data collected at Day 1 will be assigned to the screening period. However, adverse events and concomitant medications starting on Day 1, will be assigned to the Treatment Period, unless the time (HH:MM) demonstrates otherwise.

The Treatment Period is defined as the period from the date/time of the first dose of study drug to Week 32 (four weeks after the last dose) or early termination/end of treatment visit (within two weeks from the last dose).

Treatment will be divided into two periods, Period 1 and Period 2. In Part B, Period 1 will start at the first dose of study drug and end at Week 16 when Week 16 assessments are completed and before administration of study drug. Period 2 will start at the time of first administration of study drug at or after Week 16 and end at Week 32 or early termination/end of treatment visit.

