6.7.3. Laboratory Evaluations

Data for the following hematology, clinical chemistry, routine urinalysis, pregnancy testing, other screening tests, and other tests analytes received from the central laboratory are to be measured at the scheduled timepoints (Baseline, Week 4, 8, 12, 16, 24, 32, and 39).

Table 1 Laboratory Tests

Laboratory Tests	Parameters				
Hematology	Platelet count Red blood cell (RBC) count Hemoglobin Hematocrit	RBC indice Mean corpu (MCV) Mean corpu hemoglobin %Reticuloc	scular volume scular (MCH)	with Neu Lyn Mor Eosi	te blood cell (WBC) count a differential: trophils phocytes nocytes inophils ophils
Clinical chemistry1	Blood urea nitrogen (BUN)	Potassium	Aspartate aminotransfer (AST)/serum glutamic- oxaloacetic transaminase (SGOT)		Total and direct bilirubin
	Creatinine	Sodium	Alanine aminotransfer (ALT)/serum glutamic-pyru transaminase (SGPT)		Total protein
	Glucose (non-fasting)	Calcium	Alkaline phosphatase ₂		Fasting lipid (total cholesterol, triglycerides & HDL)
Routine urinalysis	 Specific gravity pH, glucose, protein, blood, ketones, by dipstick Microscopic examination (if blood or protein is abnormal) 				
Pregnancy testing Other screening tests	 Highly sensitive serum human chorionic gonadotropin (hCG) pregnancy test (as needed for women of childbearing potential) at screening Follicle-stimulating hormone and estradiol (as needed in women of nonchildbearing potential only) Serology hepatitis B surface antigen (HBsAg), and hepatitis C virus antibody Tuberculosis testing: QuantiFERON® test or purified protein derivative (PPD) test Note: T-SPOT® tuberculosis test may be acceptable if agreed upon with the medical monitor 				

In accordance with the baseline value definition in Section 5.1.2, the change from baseline will be derived as follows:

Change (unit) = (post-baseline value – baseline value)

All laboratory data will be reported in SI units. All quantitative laboratory test values at each assessed timepoints (Baseline, Week 4, 8, 12, 16, 24, 32, and 39) will be compared with the relevant reference range in SI units and categorized as:

- Low: Below the lower limit of the reference range.
- Normal: Within the reference range (upper and lower limits included).
- High: Above the upper limit of the reference range.

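### The symptom review behind the sixth liver criterion excludes anyone who meets criteria 1 to 5, so the Kaplan-Meier analysis of symptomatic ALT/AST elevation undercounts its own endpoint

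*SAP*

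**What the plan says.** All of this is in SAP section 6.7.3.1 (Liver toxicity review).

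- **Listing.** "Subjects who met any (one or more) of the following criteria will be included in a listing for consideration of DILI". In short, the criteria are: (1) ALT or AST at least 5 x ULN; (2) at least 3 x ULN persisting over 4 weeks or more; (3) at least 3 x ULN with bilirubin at least 2 x ULN and more than 35% direct; (4) at least 3 x ULN with INR at least 1.5; (5) at least 3 x ULN without weekly tests for at least 4 weeks afterwards; (6) at least 3 x ULN "associated with symptoms (new or worsening) believed to be related to liver injury or hypersensitivity at any time".
- **How criterion 6 is decided.** "To determine subjects who meet the last criterion, a listing of all subjects who have at least one ALT or AST" of at least 3 x ULN, "and who do not meet any of the first five criteria, will be reviewed by qualified medical professionals", together with their adverse events. The result goes into a memo filed before lock and unblinding.
- **Listing content.** All liver results and the treatment assignment, "along with specific criterion met".
- **Kaplan-Meier analyses.** Five endpoints: Hy's Law and criteria 1, 3, 4 and 6. Criterion 6 appears in the same words as in the listing, with no condition that the other criteria be absent. Subjects without an event are censored at the last assessment attended. Product-limit estimates are given at Weeks 16 and 32, and an analysis is not done if an arm has fewer than 3 events.

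**The concern.** The restriction is a sensible shortcut for one purpose and a defect for two others. To decide who enters the listing, nobody needs to know whether a subject who already meets criterion 1 was also symptomatic. To estimate time to first symptomatic elevation, and to fill the criterion column, that is exactly what must be known.

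The SAP gives no other step for establishing criterion 6. A subject with symptoms and ALT of 6 x ULN therefore has no route to becoming an event in the analysis named for symptomatic elevation. Because the excluding criteria apply over the whole study, a subject who is symptomatic at 3.5 x ULN and only later meets the persistence criterion is dropped as well. At stake is a by-arm safety estimate that does not measure what its label says.

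**Working it through.** The plan states no figure on this point, so there is none to reproduce. The check is a comparison of the rules, followed by an illustration.

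**1. Which symptomatic subjects can be counted.** Take a subject with a true symptomatic ALT or AST of at least 3 x ULN. Each of criteria 1 to 5 is met or not, giving 2^5 = 32 profiles.

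| Rule | Profiles that can be counted as symptomatic |
|---|---|
| Review as written (none of criteria 1 to 5 met) | 1 of 32 |
| Review of everyone with ALT or AST at least 3 x ULN | 32 of 32 |

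The profiles are not equally likely, so 1 in 32 is a count of logical cases and not a capture rate.

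**2. Which excluded subjects have another liver curve.** Criteria 1, 3 and 4 have their own; criteria 2 and 5 do not. Of the 31 excluded profiles, three meet only criterion 2, only criterion 5, or only both. A symptomatic subject in one of these has no other curve, unless Hy's Law is met with bilirubin at or above 2 x ULN but a direct fraction of 35% or less.

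**3. Direction of the error.** Replacing an event by a later censoring time removes a factor below 1 from the product-limit estimate and leaves the risk sets no smaller. The estimated incidence in each arm can only fall. The effect on the difference between arms depends on each arm's share of excluded cases, which the documents do not give.

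**4. The protocol does not make criterion 6 conditional.** In protocol section 10.5 the symptomatic criterion stands on its own line. The monitoring instructions for raised bilirubin or INR apply with or without symptoms, so overlap is expected. The same section has liver and hypersensitivity symptoms recorded on the CRF.

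**5. Criterion 5 can remove further subjects.** Scheduled chemistry after baseline falls at Weeks 4, 8, 12, 16, 24, 32 and 39, that is, 4 to 8 weeks apart. Protocol section 10.5 also lets retesting drop to weekly or less often once abnormalities stabilize. A subject followed as the protocol allows may lack weekly tests for 4 weeks and so leave the review. How many would is unknown.

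**6. Illustration under assumptions that are not in the documents.** Suppose one izokibep arm of 56 has S truly symptomatic subjects, and each independently meets at least one of criteria 1 to 5 with probability q. The number counted is Binomial(S, 1 - q).

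With S = 4, P(at least 3 counted) = 4(1 - q)^3 q + (1 - q)^4:

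| q | Expected count, 4(1 - q) | P(at least 3 counted) |
|---|---|---|
| 25% | 3.0 | 0.422 + 0.316 = 74% |
| 50% | 2.0 | 0.250 + 0.0625 = 31% |
| 75% | 1.0 | 0.047 + 0.004 = 5% |

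All four true events would have met the minimum. With S = 6 and q = 50%, crude incidence falls from 6/56 = 10.7% to an expected 3/56 = 5.4%.

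**The case against.** The strongest reply is that little is lost. Every affected subject stays in the listing with all liver results and treatment assignment. Hy's Law, the 5 x ULN threshold, bilirubin and INR each have their own curve, and related adverse events appear in the by-arm TEAE tables. No hypothesis test depends on this analysis. The protocol has symptoms recorded on the CRF, so the information should exist and only a link in the SAP is missing. An arm with fewer than 3 true events would have no analysis under any rule. All of this stands, and it limits the point to one Kaplan-Meier analysis and one column. It does not remove the mismatch, because the SAP does not use the CRF symptom data to establish criterion 6.

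A reader might go further in four ways that the documents do not support.

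- *Only the mildest cases are counted, and izokibep harm is understated overall.* Criteria 2 and 5 concern persistence and missing follow-up and are not severity grades. The severe findings are reported elsewhere, as above.
- *The listing would call severe cases asymptomatic.* The column shows the criteria met. Criterion 6 would be omitted, not reported as negative.
- *The reviewed set would be almost empty.* Nothing in the documents gives its size.
- *Stopping the liver curves at Week 32 hides late cases.* The window, "for the study duration (Day 1 through Week 32"), is an openly stated choice for a descriptive plot. SAP section 6.7.3 also summarizes chemistry at Week 39, and the liver listings cover the whole study. For the Hy's Law Period 2 table, section 5.1.3 has Period 2 start "at or after Week 16 and end at Week 32 or early termination/end of treatment visit", but section 6.7 gives no end date for Period 2 data other than adverse events. Week 39 is 56 days (QW) or 63 days (Q2W) after the last dose. With the protocol's 278 h half-life (11.6 days), simple decay leaves 0.5^(56/11.6) = 3.5% or 0.5^(63/11.6) = 2.3% of drug.

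**Conclusion.** The concern holds for the symptomatic-elevation Kaplan-Meier analysis and for the listing's criterion column. The step that establishes criterion 6 excludes subjects whom the endpoint, as defined, includes. The Week 16 and Week 32 incidence estimates can therefore only be too low, and the analysis may be dropped in an arm that truly had 3 or more events. The column will be incomplete for symptomatic subjects who meet any other criterion.

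The conclusion assumes that the SAP is applied as written, with no unstated use of the CRF symptom data. The size of the undercount cannot be computed from the documents, and the figures in step 6 show the mechanism only. The remaining liver outputs are unaffected, although symptomatic subjects who meet only criterion 2 or 5 will generally appear in no liver curve. It should be corrected because the plan contradicts itself and the correction is cheap, not because the liver safety report as a whole is unreliable.

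**What to change.** In SAP section 6.7.3.1:

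1. Delete the clause limiting the review to subjects who meet none of the first five criteria, so that the review before lock and unblinding covers every subject with any ALT or AST at least 3 x ULN.
2. State that the review uses both the adverse events and the liver and hypersensitivity symptoms recorded on the CRF under protocol section 10.5.
3. For each reviewed subject, record in the memo whether the elevation was associated with symptoms and the first date on which it was.
4. Use that record both for the listing's criterion column and for the events and event times in the Kaplan-Meier analysis.

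If the sponsor prefers to keep the restriction, the Kaplan-Meier endpoint should be relabelled as symptomatic elevation in subjects who meet no other criterion. That is the weaker option, because it leaves symptomatic elevation overall unreported.

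The cost is a change of wording and a few more subjects' listings to read. The memo is already planned, no new data are needed, and no clinical rule changes.
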